Figure 5. Trisomy 21 induces the kynurenine pathway. **A.** Volcano plot showing results of a plasma metabolomics experiment on 120 participants, 72 of them with T21. **B.** Overview of tryptophan catabolism pathways. **C.** Quinolinic acid (QA) is significantly elevated in plasma of people with DS. **D.** RNA-seq shows that *IDO1* is overexpressed in white blood cells from people with DS. **E.** Spearman correlation analyses revealed strong association between activation of the kynurenine pathway and circulating levels of cytokines such as TNF α measured in the same plasma

neuroinflammatory phenotype of DS (90-98) may have therapeutic benefits, even in adults. Given the well-documented negative impact of hyperactive IFN signaling on brain function, from excessive synapse pruning by IFN-activated microglia to global impairments in cognitive function upon acute IFN α administration (99-106), **we hypothesize that reducing IFN signaling via JAK inhibition could improve cognition and behavior regulation in DS**. Of note, Tofacitinib was shown to cross the blood-brain barrier in mice (107). Thus, we will assess changes in selected cognition and overall quality of life metrics for individuals with DS upon JAK inhibition.

IV. Research Methods

B. Outcome Measure(s):

Name. Evaluate the safety of Tofacitinib in people with DS.

Type. Primary Endpoint.

Time Frame. Baseline through 16 weeks.

Brief Description. Adverse events (AEs) will be recorded, classified, and closely monitored by study coordinators and doctors. Based on published safety data, we calculate that we should have no more than two serious adverse events (SAE) definitely related to treatment over the course of 16-weeks in order to demonstrate comparable safety to the typical population.

Name. Change in IFN scores in the transcriptome of white blood cells.

Type. Primary Endpoint.

Time Frame. Baseline and 16 weeks.

Brief Description. Using published methods, IFN scores will be calculated using RNA-seq from whole blood RNA. A two-sided, paired Student's t-test will be used to determine the significance of any changes observed.

Name. Change in IGA.

Type. Secondary Endpoint.

Time Frame. Baseline and 16 weeks.

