IFN transcriptional scores. We will monitor the impact of Tofacitinib on WBC IFN transcriptional scores for each participant at baseline and at 16 weeks of treatment. Additional time points will be collected and processed in a fashion compatible with future analysis, and skin tape samples will be banked for future cytokine analysis. IFN scores have been developed for IFN-driven conditions such as SLE and Type I Interferonopathies (69-71), and consist of a composite Z-score that integrates mRNA expression values for multiple ISGs into a single numerical value that can be used to track correlations with disease severity (71), and which have also proven effective to monitor the impact of JAK inhibition in clinical trials (69). Using published methods (69-71) we observed significantly higher Type I IFN scores in both T cells (*Figure 3C*) and total WBCs (110). Thus, we clearly have the expertise to monitor changes in IFN signaling with this approach. Much of this protocol has been described in our previous publication (27). RNAs will be extracted using the PAXgene Blood RNA Kit and quality assessed using the Agilent 2100 Bioanalyzer System. Next-generation sequencing libraries will be prepared with the Illumina TruSeq Stranded mRNA Library Prep Kit and sequenced with an Illumina NovaSeq 6000 instrument. Analysis of library complexity and high per-base sequence quality across all reads will be performed using FastQC software. Other bioinformatic steps include trimming of low-quality bases, short reads, and adaptor sequences, with the fastqc-mcf tool; removal of mycoplasma, mitochondria, and rRNA contaminant sequences with FASTQ Screen; read alignment to GRCh37/hg19 using TopHat2; filtering of high-quality mapped reads with SAMtools; and final quality performed using RSeQC. Gene level counts will be then obtained using HTSeq (111). IFN scores will be calculated by adapting methods described in the literature (69-71), using RPKM values instead of values derived from Nanostring or q-RT-PCR data. We define success of this endpoint as statistically significant reduction in average IFN scores between baseline and 16 weeks as defined by a two-sided, paired Student's t-test.

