The potential risks associated with participation in the study center largely around the usage of Tofacitinib. Increased risks associated with taking Tofacitinib include: development of serious infections and sometimes fatal infections, especially in participants taking concomitant immunosuppressants; development of solid tumor cancer; laboratory abnormalities such as lymphocytosis, neutropenia, anemia, elevated liver enzymes, elevated lipids, elevated serum creatinine, and elevated blood creatine phosphokinase; nasopharyngitis; diarrhea; headache; rash; nausea; and hypertension. Additional risks may include gastrointestinal perforation. These risks will be addressed in the informed consent form.

To mitigate these risks, the design of the inclusion and exclusion criteria, as well as the study visit timeline and safety monitoring labs, have been optimized to meticulously protect participants. Individuals with any active infection and those taking concomitant immunosuppressants will be excluded from the study due to the increased risk of developing severe infections. Individuals with any history of malignant solid tumor cancers will be excluded from the study due to the increased risk of developing a malignancy. Safety monitoring will be performed at each visit to ensure participants do not develop infections or unsafe levels of cell counts, liver enzymes, lipids, creatinine, and creatine phosphokinase. Participants will see a study doctor at each of the eight visits to monitor overall health and ensure any other side effects, such as headache, nausea, diarrhea, or high blood pressure are appropriately managed and reported.

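### The primary IFN score rests on RPKM with no stated globin exclusion or composition-robust scaling; if the specimen is whole blood, a shift in red-cell RNA share could pass for, or mask, a drug effect

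*Combined protocol and SAP*

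**What the plan says.** **Specimen.** Section IV, Outcome Measure(s), names the endpoint "Change in IFN scores in the transcriptome of white blood cells", but its description reads "Using published methods, IFN scores will be calculated using RNA-seq from whole blood RNA". Research Methods for Specific Aim 2 speaks of white-cell scores, yet its pipeline begins: "RNAs will be extracted using the PAXgene Blood RNA Kit and quality assessed using the Agilent 2100 Bioanalyzer System". Section V, Description of Procedures, says that the laboratory separates plasma, white cells and red cells, and it lists RNA-seq as a white-cell dataset.

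**Processing.** Specific Aim 2 continues: "Next-generation sequencing libraries will be prepared with the Illumina TruSeq Stranded mRNA Library Prep Kit". The reads filtered out are given as "removal of mycoplasma, mitochondria, and rRNA contaminant sequences with FASTQ Screen". Gene-level counts come from HTSeq. The score is a "composite Z-score that integrates mRNA expression values for multiple ISGs into a single numerical value", adapted from cited methods "using RPKM values instead of values derived from Nanostring or q-RT-PCR data". Part of the RNA-seq protocol is left to an earlier publication. Globin depletion, exclusion of globin reads, composition-robust size factors and adjustment for blood counts are not mentioned.

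**Test.** Section VII, Specific Aim 2, defines success as a significant reduction on a two-sided paired t-test, with 80% power at an effect size of 0.45 in 40 participants.

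**The concern.** RPKM divides a gene's reads by the library total and by gene length. In an mRNA library made from whole blood, part of that total can be globin message from red cells. If the globin part grows or shrinks relative to white-cell RNA, every other gene's RPKM moves by the same factor although interferon signalling has not changed. Averaging several interferon genes does not cancel a factor that they all share, and neither does a log transform.

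Pairing removes stable differences between people, but not a mean change over time, and there is no control arm in which such a change would show. The risk section gives some reason to expect blood composition to move on treatment: it lists "laboratory abnormalities such as lymphocytosis, neutropenia, anemia" among possible drug effects. The paired t-test on this score is the only formal test of a primary efficacy endpoint, so an artefact here acts directly on the trial's main efficacy claim.

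**Working it through.** **1. The plan's own figure.** Inputs from section VII: n = 40, effect size 0.45, two-sided alpha 0.05. Noncentral t with df = 39, noncentrality 0.45 × √40 = 2.846 and critical value 2.023 gives power 79.3%. The stated 80% reproduces. With no effect, the chance of a significant reduction is 2.5%.

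**2. The common factor.** Let g be the globin share of reads at baseline and c the fold change in globin RNA, with all other RNA unchanged. Each non-globin RPKM is multiplied by

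F = 1 / ((1 − g) + g·c).

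For g = 0.6: c = 0.8 gives 1/(0.4 + 0.48) = 1.136, and c = 1.2 gives 1/(0.4 + 0.72) = 0.893.

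**3. From factor to effect size.** The SD of the paired change is not in the documents. I take a log-scale score and set the SD so that 0.45 corresponds to a true fall of 20% or of 40%:

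- 20% fall: SD = −ln(0.8)/0.45 = 0.496
- 40% fall: SD = −ln(0.6)/0.45 = 1.135

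The artefact in effect-size units is ln(F)/SD. It is added to −0.45 to get power, and to 0 to get the false-reduction rate.

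Worked case, g = 0.6, SD = 0.496:
- c = 0.8: ln(1.136) = 0.128, and 0.128/0.496 = 0.258. The effect becomes −0.45 + 0.258 = −0.192, and power is 22%. On the ratio scale, a true 20% fall reads as 1 − 0.8 × 1.136 = 9%.
- c = 1.2: ln(0.893) = −0.113, and −0.113/0.496 = −0.229. With no drug effect, a significant reduction appears 29% of the time.

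**4. Results at g = 0.6** (first value: 0.45 is a 20% fall; second: a 40% fall).

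| Mean change in globin RNA | F if it falls | Power | F if it rises | False reduction |
|---|---|---|---|---|
| 5% | 1.031 | 67% / 74% | 0.971 | 5.6% / 3.6% |
| 10% | 1.064 | 52% / 68% | 0.943 | 11% / 5% |
| 20% | 1.136 | 22% / 55% | 0.893 | 29% / 9% |

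At g = 0.4 and a 20% change, the same formulas give power 41% / 64% and false reduction 16% / 6%.

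**5. A second parametrisation.** Suppose the globin share itself moves 5 points from 50%, with an SD of 0.5 to 1.0 log2 units. A rise to 55% gives F = 0.45/0.50 = 0.90 and a false-reduction rate of 15–47%. A fall to 45% gives F = 0.55/0.50 = 1.10 and power of 19–49%. That rise corresponds to c = 0.55/0.45 = 1.22, so it is comparable to the 20% row and not a small shift.

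**6. Random change only.** If the share varies within people with no mean shift, there is no bias. Extra variance of 10% to 30% reduces the effect size to 0.45/√1.1 = 0.429 or 0.45/√1.3 = 0.395, with power 75% or 68%.

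**The case against.** The strongest reply concerns the specimen. The endpoint name, the text of Specific Aim 2 and section V all refer to white cells, and section V describes separation before RNA-seq. If that is what happens, globin share hardly matters. This stands: the point is conditional. It does not dispose of the matter, because the endpoint description says whole blood and the only detailed pipeline names a blood RNA kit.

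A reader might infer that the plan rules out globin removal, or that it has no between-sample scaling at all. Neither is supported. The documents are silent on globin and defer detail to cited work that cannot be checked here, so the accurate wording is that none is specified. RPKM does scale for sequencing depth; what is unstated is scaling robust to RNA composition. The citations do not settle that, since the plan adapts those methods and substitutes RPKM for their expression values.

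A reader might also infer that the listed anemia and neutropenia show a systematic bias of known direction. They do not. In this model a loss of red-cell RNA raises the interferon-gene values and a loss of white-cell RNA lowers them. The risk section gives no frequency or size, and no passage links hemoglobin to globin RNA. Neutropenia and lymphocytosis are changes in white-cell mix, which is a different problem. Clinically significant abnormal laboratory findings are also among the individual stopping rules, which may limit extreme values among completers. The net direction and size are therefore open.

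**Conclusion.** The point holds in conditional form. If the RNA is from whole blood, the stated scaling leaves the primary score exposed to a common shift that this design cannot detect, in either direction. If white cells are separated first, the exposure is largely gone. The documents support both readings and must be reconciled.

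The size is not established. Globin share, mean shift and SD of change are all assumptions. The illustration runs from minor (a 5% shift) to serious (a 20% shift), and the serious end requires a cohort-mean change that nothing in the documents demonstrates. It would be wrong to read the figures as showing that the primary result will be biased. What they show is that the present choice carries an avoidable risk on the only primary efficacy test, while a more robust method is available from counts already planned.

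**What to change.** 1. State one specimen in the outcome list, Research Methods for Specific Aim 2 and section V.
2. In Specific Aim 2 and in section VII, compute the score from the planned HTSeq counts: exclude globin genes, apply median-of-ratios or TMM size factors, take log2, then form the Z-score. Fix this, with the gene list and the Z-score reference, before the primary analysis.
3. Keep the RPKM score as a sensitivity analysis.
4. Add a sensitivity analysis that uses change in the blood counts collected at every visit (Table 2). Size factors do not correct changes in white-cell mix, and this analysis can address them.

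Excluding globin from the scaling removes the common red-cell shift and returns the design to its 79% power and 2.5% false-reduction rate, under the plan's own assumptions. The cost is one bioinformatics step, some plan wording and slightly less direct comparability with earlier RPKM-based scores. No new sample or assay is needed.

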Informed consent and assent forms will also be obtained before or at the screening visit. After receiving results from all screening tests and confirming eligibility, a study doctor will prescribe Tofacitinib from the UCHealth or CU Anschutz Medical Center Investigational Pharmacy. We anticipate participants will return for their baseline visit within approximately four weeks of their screening visit. If the duration between Screening and Baseline visit is longer than 4 weeks, study doctors may order screening labs again at their discretion. At the baseline visit, participants will be instructed to begin administration of oral Tofacitinib at 5 mg BID the following morning. Study visits are timed at Time 0 (baseline), 2, 4, 8, 12, and 16-weeks throughout the course of treatment, as well as 2 weeks after ending treatment (18 weeks in total to complete study visits). Participants in the Extension Arm will have an additional visit at 28 weeks with the final follow-up visit at 40-week. Each study visit will occur +/- 3-days of this schedule determined from Time 0 (baseline), except for Extension Arm visits that will occur +/- 7 days of the ideal visit schedule. Missed study visits or visits that occur outside of this window will be reported as a protocol deviation/violation and will not change the original schedule. A missed study visit that was supposed to include dispense of Tofacitinib should be rescheduled, even if outside the allowed window. Study doctors will not continue the Tofacitinib prescription without current safety labs.

Condition	Assessment	Minimum score
Moderate-to-severe atopic dermatitis	Eczema Area and Severity Index (EASI)	≥ 16
Alopecia areata affecting at least 25% of the scalp	Severity of the Alopecia Tool (SALT)	≥ 25
Moderate-to-severe hidradenitis suppurativa	Hidradenitis suppurativa - Physician's Global Assessment (HS-PGA)	≥ 3
Moderate-to-severe Psoriasis	Psoriasis Area and Severity Index (PASI)	≥ 10
Moderate-to-severe Vitiligo	Vitiligo Extent Tensity Index (VETI)	≥ 2

Table 1. Minimum score for inclusion criteria for each skin condition.

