Each visit will entail a physical exam, collection of vital signs, recording and monitoring of adverse events (AEs, see below), and a blood draw for the same battery of safety monitoring labs described in the screening procedures above. A follow-up ECG will be performed for all participants at the 4-week visit and as needed based upon concomitant medications at the study doctor's discretion. An audiogram will be performed before beginning treatment and after 15-16 weeks of treatment, to ensure Tofacitinib has not impacted hearing. A recent audiogram performed within the past 12 months for clinical reasons can be provided or accessed by the study team will be accepted, given that the appropriate elements were evaluated and no change in hearing status is anticipated. A negative Quantiferon Gold, Quantiferon Gold Plus or Quantiferon Gold HA and chest x-ray that have been obtained for clinical reasons within the past 12 months will be accepted for screening purposes if no change in TB status is anticipated. Participants will receive a tuberculosis screen at least every 12 months while in the study. Outside laboratory results will be accepted at the study doctor's discretion (Figure 6). Every effort will be made to have the same study doctor meet with a participant at each visit to minimize interrater bias. Skin conditions will be formally assessed at screening, baseline, 8, and 16 weeks by a dermatologist using standard and accepted metrics, such as: Investigator's Global Assessment (IGA) and Dermatology Life Quality Index (DLQI) for all skin conditions, Eczema Area and Severity Index (EASI) for AD, Severity of Alopecia Tool (SALT) for AA, Modified Sartorius Score (MSS) for HS, Psoriasis Area and Severity Index (PASI) for psoriasis, and Vitiligo Extent Tensity Index (VETI) for vitiligo. Note that the Hidradenitis Suppurativa – Physician's Global Assessment (HS-PGA) will be used to determine eligibility for participants with HS at screening and for EA qualification, while the MSS will be ongoing. Photographs will also be taken of the affected area(s) at the time of these assessments for additional validation of skin condition and visual, qualitative indicators of improvement or progression. Photographs may be taken at other safety visits to document response to treatment at the study doctor's discretion. Open-source online scoring calculators may be used to calculate skin condition severity, provided no PHI is entered. Participants in the Extension Arm will also have a formal skin assessment at 28 and 40 weeks.

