On very rare occasions, research labs are unable to be collected, or are only partially collected, due to participant dehydration or poor venous blood access. For participants co-enrolled in the Human Trisome Project (15-2170), research samples may be collected using a non-invasive capillary blood Tasso device as approved in that protocol, with samples transferred to this study for research purposes. If participants choose not to enroll in the Human Trisome Project, research samples will not be collected. Follow-up blood collection for research purposes must include the same collection method as obtained at Baseline visit, if possible.

Study data is collected and recorded in both electronic and paper format. Study visit data are recorded in REDCap, a HIPAA compliant online system administered locally by CU Anschutz. Study visits utilizing the CTRC are requested through the CU-Anschutz Oncore study management system, which contains study visit schedule, visit procedures, and integrates with the electronic medical record (Epic) and financial billing. Study visit procedure details are also documented in Epic.

Combined Screening and Baseline Activities.

If all screening labs and procedures are completed so that the participant is deemed eligible and can begin tofacitinib within five days of the blood draw, the laboratory values from the Screening Visit blood draw will be used for Baseline values. In this instance, an additional Baseline blood draw or formal skin assessment will not be required, except at the study doctor's discretion.

Safety Labs Collected	Version Date Implemented	Screening Visit 1	Baseline Visit 2	2-week Visit 3	4-week Visit 4	8-week Visit 5	12-week Visit 6	16-week Visit 7	2-week post Visit 8%	28-week Visit E28	40-week Visit E40
Chest X-ray	02.20.2020	X	N/A	N/A	N/A	N/A	N/A	N/A	N/A	N/A	N/A
ECG	02.20.2020	X	N/A	N/A	X	N/A	N/A	N/A	N/A	N/A	N/A
Audiogram	02.20.2020	X	N/A	N/A	N/A	N/A	N/A	X	N/A	N/A	N/A
Pregnancy Test [^]	04.22.2021	X	X	N/A	X	X	X	E	N/A	E	N/A
Complete Blood Count (CBC)	02.20.2020	X	X	X	X	X	X	X	X	E	E
Comprehensive Metabolic Panel	02.20.2020	X	X	X	X	X	X	X	X	E	E
Lipid Panel	02.20.2020	X	X	X	X	X	X	X	X	E	E
Creatinine Phosphokinase	02.20.2020	X	X	X	X	X	X	X	X	E	E
Quantiferon TB Gold Plus	02.20.2020	X	N/A	N/A	N/A	N/A	N/A	N/A	N/A	N/A	N/A
Virology (EBV IgG/IgM, CMV IgG/IgM, VZV IgG, HIV 1 and 2, HCV, HSV Type 1 &2 IgG, Hep B Surface Antigen/Core Antibody)	02.20.2020	X	N/A	N/A	N/A	N/A	N/A	N/A	N/A	N/A	N/A

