2. Psoriasis (min. initial qualifying PASI score ≥ 10): Participants showing any decrease in their PASI score from Baseline, but PASI score is still ≥ 2 at 8-week appointment.
 - Participants with a diagnosis of psoriatic arthritis will be referred to a rheumatologist for on-label prescription.
3. Atopic dermatitis (min. initial EASI qualifying score ≥ 16): Participant showing any decrease in EASI score from Baseline, but EASI score still ≥ 5 at 8-week appointment.
4. Hidradenitis suppurativa (min. initial HS-PGA score ≥ 3): Participant showing a HS-PGA score ≥ 2 from Baseline with any concurrent decrease in Modified Sartorius Scale (MSS) at 8-week appointment or subsequent appointment. As HS may not respond during an 8-week course, all participants with HS may be invited to participate in the Extension Arm at the study doctor's discretion.
5. Vitiligo (min. initial qualifying VETI score ≥ 2): As vitiligo may not respond during an 8-week treatment course, all participants with vitiligo may be invited to participate in the Extension Arm at the study doctor's discretion.

Research Labs Collected	Version Date Implemented	Screening Visit 1	Baseline Visit 2	2-week Visit 3	4-week Visit 4	8-week Visit 5	12-week Visit 6	16-week Visit 7	2-week post Visit 8%	28-week Visit E28	40-week Visit E40
1) Thyroperoxidase (TPO) 2) Thyroglobulin (TG) 3) Thyroid stimulating hormone receptor (TRAb)	02.20.2020	X	X	*	N/A	*	N/A	X	*	*	*
tissue trans-glutaminase (tTG) IGA	04.22.2020	X	X	*	N/A	*	N/A	X	*	*	*
anti-deamidated gliadin peptide (DGP)	04.22.2020	X	X	*	N/A	*	N/A	X	*	*	*
Immunoglobulin A	04.22.2020	X	X	*	N/A	*	N/A	X	*	*	*
Skin tapes	02.20.2020 11.12.2020	N/A	X	N/A	N/A	X	N/A	X	N/A	N/A	E
Tongue swab	02.20.2020	X	X	X	N/A	X	N/A	X	X	E	E
Skin photos	02.20.2020 11.12.2020	X	X	\$	\$	X	\$	X	\$	\$	E
ESR	11.12.2020 05.26.2021	X	X	X	X	X	X	X	X	E	E
CRP	05.28.2021	X	X	X	X	X	X	X	X	E	E
DNA	04.18.2022	N/A	X	N/A	N/A	N/A	N/A	X	N/A	N/A	X

Table 3. Schedule of research labs. 'X' = Test performed; N/A = Not applicable; * Follow-up required only if Screening Visit results are positive; % This visit only occurs for participants who ended Tofacitinib treatment at Visit 7; E = Extension Arm only visits; \$ As needed to document skin changes

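### Combined screening/baseline visits make the baseline skin score optional, so for EASI, SALT, PASI and VETI the qualifying score may serve as baseline and regression to the mean would count as improvement

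*Combined protocol and SAP*

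**What the plan says.** The ordinary schedule in section IV.C (Study Visits and Activities) has two pre-treatment skin assessments: "Skin conditions will be formally assessed at screening, baseline, 8, and 16 weeks by a dermatologist using standard and accepted metrics". Baseline is expected within about four weeks of screening.

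The subsection on Combined Screening and Baseline Activities sets an exception. Its condition, counted from the screening blood sample, is: "If all screening labs and procedures are completed so that the participant is deemed eligible and can begin tofacitinib within five days". When this is met, "the laboratory values from the Screening Visit blood draw will be used for Baseline values". On repeating the assessments the rule reads: "In this instance, an additional Baseline blood draw or formal skin assessment will not be required". The waiver is not absolute, since it goes on to leave the choice open: "formal skin assessment will not be required, except at the study doctor's discretion". Only laboratory values are named as carried over. Nothing says which skin score is then the baseline.

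Table 1 ("Minimum score for inclusion criteria for each skin condition") requires EASI of at least 16, SALT of at least 25, PASI of at least 10 or VETI of at least 2 for four of the five named conditions. Hidradenitis suppurativa (HS) qualifies on HS-PGA (at least 3) but is followed on the Modified Sartorius Score (MSS). IGA and DLQI have no entry threshold, and DLQI is also listed with the PROMIS forms at the baseline visit.

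All participants receive tofacitinib, open label. The Data Analysis Plan (Specific Aim 3) compares baseline with week 16 by a two-sided paired t-test. Success is a significant percentage reduction in at least one of IGA, DLQI and the disease-specific scores. The Research Methods for Specific Aim 3 make skin improvement the leading secondary endpoint.

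**The concern.** A participant admitted because a reading crossed a threshold will, on average, score lower next time even if nothing has changed. A second score that plays no part in eligibility protects the change score from much of this. The ordinary schedule provides one, and the combined-visit rule makes it optional.

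Without a control arm, the expected fall cannot be separated from drug effect, and its direction is always towards apparent improvement. Because one significant metric is enough for success, one inflated disease-specific score matters. The plan also pools percentage reductions across conditions, so participants with a selected baseline would be mixed with participants whose baseline was re-measured. The documents contain no adjustment for this and no sensitivity analysis for combined visits.

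**Working it through.** **1. The plan's own figure.** For 40 participants, effect size 0.45 and two-sided alpha 0.05, the noncentrality is 0.45 × √40 = 2.85 on 39 degrees of freedom. Exact power is 79.3%, against 80% stated. The figure reproduces and is not in question. With no drug effect and no selection, the chance of a significant *reduction* is 2.5%.

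**2. Which scores are exposed.**

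| Condition | Qualifies on | Endpoint | Same score? |
|---|---|---|---|
| Atopic dermatitis | EASI ≥ 16 | EASI | yes |
| Alopecia areata | SALT ≥ 25 | SALT | yes |
| Psoriasis | PASI ≥ 10 | PASI | yes |
| Vitiligo | VETI ≥ 2 | VETI | yes |
| HS | HS-PGA ≥ 3 | MSS | no |
| All | no threshold | IGA, DLQI | no |

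The last two rows are exposed only through correlation with the qualifying severity.

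**3. Expected fall with no drug effect.** Let the score have mean μ and SD σ among those screened, entry threshold c, and correlation r between two readings. Then:
- a = (c − μ)/σ and λ = φ(a)/(1 − Φ(a))
- mean qualifying score = μ + σλ
- spurious fall = (1 − r)σλ
- SD of change = σ√[(1 − r)²V + 1 − r²], with V = 1 − λ(λ − a)
- d = fall / SD of change

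The threshold of 16 is from Table 1. Everything else is assumed, since the documents give no mean, SD or repeatability for any skin score. Two distributions are used: mean 14 with SD 8, and mean 20 with SD 10.

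- Mean 14, SD 8: a = 0.25, λ = 0.964, V = 0.3125, mean qualifying score 14 + 8 × 0.964 = 21.7. With r = 0.8 the fall is 0.2 × 8 × 0.964 = 1.54, the SD of change is 8 × √(0.04 × 0.3125 + 0.36) = 4.88, and d = 0.32.
- Mean 20, SD 10: a = −0.4, λ = 0.562, V = 0.4595, mean qualifying score 20 + 10 × 0.562 = 25.6. With r = 0.9 the fall is 0.1 × 10 × 0.562 = 0.56, the SD of change is 10 × √(0.01 × 0.4595 + 0.19) = 4.41, and d = 0.13.

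| Mean, SD | r | Fall, % of baseline | d | P(significant fall), all 40 waived |
|---|---|---|---|---|
| 14, 8 | 0.8 | 7.1% | 0.32 | 50% |
| 14, 8 | 0.9 | 3.6% | 0.22 | 27% |
| 20, 10 | 0.8 | 4.4% | 0.18 | 20% |
| 20, 10 | 0.9 | 2.2% | 0.13 | 12% |

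**4. Partial use.** If a fraction f uses the waiver and the rest have a re-measured baseline with independent noise, the mean change is f × fall. Its variance is f × (SD of change)² + (1 − f) × 2σ²(1 − r) + f(1 − f) × fall². For mean 14, SD 8, r = 0.8 and f = 0.5, the mean is 0.77, the variance is 11.9 + 12.8 + 0.6 = 25.3, and d = 0.77/5.03 = 0.15. Over the four rows above:

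| Share using the waiver | P(significant fall), nominal 2.5% |
|---|---|
| a quarter | about 4% to 7% |
| half | about 6% to 16% |
| all | about 12% to 50% |

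For a quarter, the pooled spurious fall is 2.2%/4 to 7.1%/4, or 0.5% to 1.8% of baseline.

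**5. Wider assumptions.** Take 50% to 75% of those screened as selected (the plan's 25% to 50% screen-failure range, used as a rough stand-in for selection on severity) and a correlation of 0.5 to 0.9. The ranges become about 3% to 9% (a quarter), 5% to 23% (half) and 9% to 77% (all).

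**6. What a repeat score achieves.** With independent visit-to-visit noise, the rate returns to about 2.5%. If readings days apart agree better than readings 16 weeks apart, some bias stays. Take 61% selected (47 of 77 screened) and a 16-week correlation of 0.7. Using the screening score gives about 35%. A repeat score brings this to 7% if the short-interval correlation is 0.8, or 17.5% if it is 0.9.

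**The case against.** The strongest reply is that this is an optional exception with a small likely effect. The study doctor can still order the score. Using the exception requires every eligibility result in time for drug to start within five days, whereas the plan expects a gap of up to about four weeks, so use may be uncommon. HS, IGA and DLQI are not selected on their own score, and neither primary endpoint uses skin scores. The calculation treats all 40 participants as EASI-like in a trial of at least five conditions, and tests absolute change where the endpoint is percentage reduction. Natural course and unblinded rating stay uncontrolled whatever is done about the waiver.

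All of this stands as a limit on scope and size. It does not remove the mechanism. The discretion has no criteria, the share of combined visits is not stated, and if no score is ordered no other pre-treatment score exists for four instruments.

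A reader might go further in three ways that the documents do not support:
- That the plan *states* the screening skin score is the baseline. Only laboratory values are named; the skin carry-over is an inference.
- That every skin endpoint is affected alike. The direct effect is confined to EASI, SALT, PASI and VETI.
- That 12% to 50% is the trial's false-positive rate. That is the limiting case in which all 40 use the waiver.

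**Conclusion.** The point holds within limits. In a combined visit with no discretionary skin assessment, the qualifying EASI, SALT, PASI or VETI score is by inference the baseline, and regression to the mean is counted as improvement in a single-arm trial. The direction is certain but the size is not. The partial-use figures in the working are the relevant ones, and they rest on an assumed EASI-like score, normal distributions and absolute change. Lower repeatability gives larger figures. This is an inexpensive improvement to a secondary endpoint. It does not invalidate the trial and does not touch the stated power.

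**What to change.** - Limit the combined-visit waiver to the blood draw. Keep the scheduled disease-specific score and IGA, taken on a day after the qualifying assessment and before the first dose, and name that score as the baseline value. The separate day matters, because a same-day re-score by the same rater is not an independent reading.
- Confirm that DLQI at the baseline visit is outside the waiver.
- Where only a screening score exists, flag those participants, state how many there are, and repeat the disease-specific skin analysis without them.
- Report the screening-to-baseline change in everyone with both scores, as an internal, pre-drug estimate of short-interval regression to the mean.

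The cost is one already scheduled score for the participants concerned and one sensitivity analysis. Anyone who would otherwise attend only once would need a second attendance; if that is not feasible, the flag and sensitivity analysis cover them. If recruitment has finished, the flag, the sensitivity analysis and the screening-to-baseline report need no new data. The change reduces the bias but does not remove a slow flare that resolves over the 16 weeks.
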